### Secondary endpoint hypothesis:

*Null hypothesis*: No difference in self-reported benefit for the Lexie self-fit group (p1) at 2- and 6-weeks and audiologist fit hearing aids (p0) using the International Outcome Inventory for Hearing Aids (IOI-HA), i.e., p1 = p0

Alternative hypothesis (2-sided): The self-reported improvement (IOI-HA) of the Lexie self-fit group (p1) at 2- and 6-weeks will be non-inferior to the audiologist fit group, within 1 point on all scales (smallest observable difference on each scale). i.e.,  $p0 - p1 \le 1$ . This non-inferiority margin (- $\Delta$ NI) was decided based on the critical difference score reported for the IOI-HA  $^4$ .

*Null hypothesis:* No difference in speech recognition in noise (QuickSIN and DIN) improvement between the Lexie self-fit group and audiologist-fit group at 2- and 6- weeks), i.e., p1 = p0

Alternative hypothesis: The improvement of speech recognition in noise for the Lexie self-fit group at 2- and 6- weeks will be non-inferior to the audiologist-fit hearing aid using the QuickSIN and digits-in-noise test (DIN), within 1.8 dB SNR. The non-inferiority margin ( $-\Delta$ NI) is based on the critical difference score of the QuickSIN  $^5$ , i.e.,  $p0 - p1 \le 1.8$ .

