### 3.3. Sample size

This study aims to recruit 60 people (approximately 30 people in each group) with parallel allocation to the self-fit and audiologist fit groups. Sample size estimation is based on a previous OTC trial conducted by Sabin et al. 2020, who recruited similar sample sizes .

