# 5. Statistical analyses

# 5.1. Level of statistical significance

Final analyses of the primary and secondary outcomes will be analysed using a two-sided significance level of 5%.

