# Self-reported hearing aid difficulties

Primary endpoint analyses include the self-reported benefit using the APHAB. Benefit is determined by calculating the APHAB scores conducted at the aided assessment (2-week and 6-week follow-ups) from the baseline scores. The primary endpoint data for all the scores measured at all time points (raw scores), along with the calculated benefit scores (unaided-aided) will be continuous variables. Data will be assessed for normality using the Shapiro Wilk's test. For non-normally distributed variables, non-parametric comparisons between groups will be completed using the Mann Whitney *U* test. For normally distributed variables, comparisons will be done using the independent samples *t*-test.

Effect sizes will be calculated for normally distributed variables, where differences were significant. Cohen's *d* is the primary metric for determining effect sizes of normally distributed variables, for which the values of 0.8, 0.5 and 0.2 are interpreted as large, medium and small effect sizes, respectively. The following formula will be used:

$$d = \frac{M1 - M2}{SDpooled}$$

Effect sizes for non-normally distributed variables will be calculated using effect size *r* for non-parametric tests, calculated using the following formula:

$$z/\sqrt{N}$$

IOI-HA (secondary endpoint) will be conducted at 2- and 6-weeks post hearing aid fitting. IOI-HA data are ordinal response categories and will, therefore, be analysed using non-parametric Mann Whitney U tests for comparison between the two groups.

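### The IOI-HA non-inferiority claim has a 1-point margin, but the only planned test (Mann-Whitney U for a difference) never uses it, so the analysis cannot establish the claim

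*Combined protocol and SAP*

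**What the plan says.** Section 4.3 (secondary endpoint hypothesis) sets the null as no difference, "using the International Outcome Inventory for Hearing Aids (IOI-HA), i.e., p1 = p0", where p1 is self-fit and p0 is audiologist-fit. The alternative is that self-fit is non-inferior at 2 and 6 weeks "within 1 point on all scales (smallest observable difference on each scale"), expressed as p0 − p1 ≤ 1. The margin "was decided based on the critical difference score reported for the IOI-HA".

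Section 5.3 gives the analysis in one sentence: "IOI-HA data are ordinal response categories and will, therefore, be analysed using non-parametric Mann Whitney U tests for comparison between the two groups". Section 5.1 sets a "two-sided significance level of 5" per cent. On size, section 3.3 says: "This study aims to recruit 60 people (approximately 30 people in each group"). It bases this on an earlier trial "who recruited similar sample sizes", with no power, SD or expected difference.

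No section names a summary measure for the IOI-HA difference, a confidence interval, a margin-shifted test, or the result that would count as non-inferior.

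**The concern.** A non-inferiority claim needs a null that self-fit is worse by at least the margin, and a result that rejects it. Here the null is equality and the test addresses equality. A significant result says the arms differ, not by how many points. A non-significant result does not show that the deficit is below 1 point.

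Whoever analyses the data must therefore choose how to apply the margin afterwards. The choice matters because the margin equals one full step on each scale and the inequality includes the boundary. Under some readings, an arm a whole category worse would often be declared non-inferior, and the planned U test could find self-fit significantly worse in the same data.

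**Working it through.** **1. Does the planned test use the margin?** There is no IOI-HA power or error figure in the plan to reproduce, so the comparison is of texts. Section 4.3 puts the claim in points. Section 5.3 gives a rank test of difference, and the effect size it offers for rank tests, r = z/√N, has no units. Section 5.4 judges whether conclusions change by p-values. Nothing links the margin to the test.

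**2. Inputs for the size of the problem.**
- From the plan: 30 per arm (3.3), margin 1 with an inclusive inequality (4.3), two-sided 5% (5.1).
- Assumed: five categories scored 1–5; three audiologist-fit distributions over scores 1 to 5, shown below; self-fit exactly one category lower throughout, so the true p0 − p1 is 1.
- 3,000–4,000 simulated trials per setting, for one scale at one visit.

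SD check for the first distribution: mean = 0.2 + 0.6 + 1.6 + 1.5 = 3.9; mean square = 0.4 + 1.8 + 6.4 + 7.5 = 16.1; SD = √(16.1 − 3.9²) = √0.89 = 0.94.

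**3. The rank-based interval.** The Hodges-Lehmann interval orders the 30 × 30 = 900 pairwise differences. The cut-off rank is 450 − 1.96 × √(900 × 61/12) = 450 − 1.96 × 67.6 ≈ 317, so the upper limit is the 584th smallest difference (900 − 317 + 1). On whole-category scores every difference is an integer, so the limit is a whole number. A limit of at most 1 then cannot separate a small deficit from a full category.

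**4. Results when self-fit is truly one category worse.** Ranges cover repeated runs, with and without tie correction of the Hodges-Lehmann limit.

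| Audiologist-fit distribution | SD | Hodges-Lehmann 95% upper limit ≤ 1 | U test p < 0.05 | Mean-difference 95% upper limit below 1 |
|---|---|---|---|---|
| 0, .10, .20, .40, .30 | 0.94 | 52%–57% | about 97.5% | 2%–3% |
| 0, .05, .10, .35, .50 | 0.84 | 73%–79% | about 99.7% | 2%–3% |
| 0, .20, .30, .30, .20 | 1.02 | 41%–45% | about 93% | 2%–3% |

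- The U test was significant and the Hodges-Lehmann limit was at most 1 in the same trial in about 35%–75% of trials.
- Point estimates are no safer: the mean difference is at most 1 in a little over half of trials, and the Hodges-Lehmann estimate in about 96%–99.8%.
- A Mann-Whitney test with 1 point added to self-fit scores, at one-sided 2.5%, passes in about 2%–3%.

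**5. The U test does not track the margin from the other side either.** With a true deficit of 0.5 point (inside the margin; SDs 0.93 and 1.05), the plain U test was non-significant in 54.9% of trials, so it was significant in 45.1%, although self-fit meets the stated claim.

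**6. Can 30 per arm support a proper test?** For a mean difference, SE = SD × √(2/30). At SD 1.02 this is 0.263, and power with identical arms is Φ(1/0.263 − 1.96) = Φ(1.84) ≈ 97%. Simulated pass rates for identical arms were about 96%–99% per scale. At 80% power and SD 1.0, the required size is 2 × (1.96 + 0.84)² × 1.0²/1² ≈ 16 per arm.

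**The case against.** The strongest reply is that section 4.3 states hypotheses about parameters, not a decision rule. Any margin puts a true difference equal to it on the boundary, and for a mean difference ≤ 1 and < 1 are almost the same. No section mentions a Hodges-Lehmann interval, so the 40%–80% describes one possible reading. This stands, and it limits the size of the finding; it does not supply the missing link between margin and test.

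A second reply is that rank methods are not at fault, since a margin-shifted Mann-Whitney test controls the error. This also stands: the ordinal approach can be kept if the shift is specified.

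A third is that the margin must hold on all scales, so the per-scale rates overstate the risk to the overall claim. Correct. Assuming 3 or 7 scales with latent correlation 0–0.7, the joint pass rate under the inclusive Hodges-Lehmann reading was 6%–52% or 0.1%–40% respectively. The documents give neither the number of scales nor their correlation.

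A reader might also infer that 1 point is a large effect on the plan's own terms, since section 5.3 gives Cohen's d benchmarks "for which the values of 0.8, 0.5 and 0.2 are interpreted as large, medium and small effect sizes, respectively". Those benchmarks are for normally distributed variables, and the same section treats the IOI-HA as ordinal, so the plan does not apply them here. Nor does it rank the IOI-HA above the speech-in-noise secondary endpoints.

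**Conclusion.** The point holds as a missing link: the margin in 4.3 and the test in 5.3 do not connect, so following the plan as written cannot validly establish IOI-HA non-inferiority. This needs no assumption beyond the text.

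A reader might go further and infer that the plan fixes a rule under which a full-category-worse arm passes, or that a false claim is likely. The documents do not support that. They state no such rule, and the pass rate runs from about 2%–3% to nearly 100% per scale depending on the rule chosen later. The 40%–80% figure applies only to an inclusive Hodges-Lehmann limit on one scale at one visit, with the five categories, SD 0.84–1.02, 30 per arm and uniform one-category shift assumed above.

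**What to change.** - **Section 4.3:** for each IOI-HA scale, state the null as p0 − p1 ≥ 1 and the alternative as p0 − p1 < 1.
- **Section 5.3:** decide each scale at each visit by a two-sided 95% confidence interval for the audiologist-fit minus self-fit difference in means, with the upper limit strictly below 1. Alternatively, use a Mann-Whitney test shifted by the margin at one-sided 2.5%. Name one of the two in advance.
- **All scales:** require success on every scale, as 4.3 already does. Keep the unshifted U test as a supporting test of difference.
- **No composite:** do not make a mean over all scales the sole decision score. Assuming 7 scales, an arm a full category worse on 3 of them has a true mean deficit of only 3/7 = 0.43, and it passed a 1-point composite rule in about 84%–99% of simulated trials.

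The cost is SAP wording; no new data are needed. The mean-difference version treats ordinal categories as scores, which a margin in points already does. Requiring every scale lowers the joint chance of success: with 7 scales assumed and 96% each, it is at least 1 − 7 × 0.04 = 72% at one visit for identical arms.

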### 4.2.1. QuickSIN

Several aspects of the QuickSIN test make it suitable for use in assessing comparable improvement of speech-in-noise performance. (1) It is designed to be presented above average conversational level (2) It uses a wide range of SNRs, and (3) the multi-talker background noise represents a common and challenging communication situation. QuickSIN is reported in terms of SNR loss, the increase in SNR required to understand speech in noise compared to persons with normal hearing; higher SNR loss indicates a poorer outcome (4).

SNR loss will be measured unaided at the initial assessment for all participants (prior to the random allocation process). Twice thereafter the aided SNR Loss will be measured. The first aided measurement as per initial fitting settings at the 3rd visit following the post 2-week field trial for the AF and SF groups. The second SNR loss will be measured with

the hearing aids set to the user's preferred setting at the 4th visit, post the 6-week field trial for both groups.

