# 4.2.2. Digits-in-Noise

Since the QuickSIN was developed in American English, one concern was that South African participants could have difficulty recognizing the words due to differences in dialect. Therefore, in addition to the QuickSIN, speech-in-noise performance will be measured using the South African English Digits-in-Noise test (DIN) (5,6). The DIN unaided and aided results will be measured following the same procedure as set for performing the QuickSIN).

Table 1. Timing of the assessments						
Visit	Baseline	Hearing Aid Fitting	2-week follow- up	6-week follow- up		
Pure tone audiometry	Х					
APHAB	X		Х	X		
IOI-HA			X	X		
QuickSIN	X		Х	Х		
DIN	X		X	X		
Real-Ear Measurement		Х		Х		

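### The 1.8 dB non-inferiority margin for the Digits-in-Noise test is justified only by the critical difference of another test, the QuickSIN

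*Combined protocol and SAP*

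**What the plan says.** Section 4.3 (secondary endpoint hypothesis) states that improvement in speech recognition in noise with the self-fit device will be non-inferior to the audiologist fit, "using the QuickSIN and digits-in-noise test (DIN), within 1.8 dB SNR". The margin for both tests "is based on the critical difference score of the QuickSIN", with one source cited for it, the QuickSIN development paper.

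Section 4.2.1 defines the first test's score: "QuickSIN is reported in terms of SNR loss, the increase in SNR required to understand speech in noise compared to persons with normal hearing". Section 4.2.2 explains why a second test was added. The QuickSIN was developed in American English, and "one concern was that South African participants could have difficulty recognizing the words due to differences in dialect". On conduct it says: "The DIN unaided and aided results will be measured following the same procedure as set for performing the QuickSIN". It does not define the DIN score or say how precise it is.

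For the IOI-HA, section 4.3 sets a margin of 1 point that "was decided based on the critical difference score reported for the IOI-HA". For the APHAB, the margin is 16.3, described as that scale's smallest observable change, although the text also calls the choice arbitrary.

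**The concern.** A critical difference describes the measurement error of the test on which it was estimated. It depends on that test's speech material, list length and scoring. Two tests that both report in dB need not share it, and one dB on each need not mean the same to a listener. The plan gives no argument that links the two tests.

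The borrowing also sits badly with the plan's own reasoning. The DIN is there because the QuickSIN may not suit these listeners, yet the QuickSIN alone sets the limit by which the DIN is to be judged.

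At stake is what the trial can conclude on the DIN. A statement that self-fitting is non-inferior on this test would rest on a limit for which the plan gives no DIN-based reason.

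**Working it through.** **Margins side by side (section 4.3)**

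| Outcome | Margin | Stated basis | Basis from the same instrument? |
|---|---|---|---|
| APHAB | 16.3 | Smallest observable change on the APHAB, called arbitrary | Yes |
| IOI-HA | 1 point | IOI-HA critical difference | Yes |
| QuickSIN | 1.8 dB | QuickSIN critical difference | Yes |
| DIN | 1.8 dB | QuickSIN critical difference | No |

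The DIN is the only outcome whose margin comes from another instrument. Section 4.2.2 aligns when and how the two tests are measured. It does not align their scores or their error.

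**Can 1.8 dB be reproduced?** No. It is a cited value, and the documents contain no inputs from which to derive it for either test. The sample size in section 3.3 rests on a precedent trial, without an SD, so it gives no indirect check.

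**What depends on the margin.** Inputs: about 30 per arm (section 3.3) and a "two-sided significance level of 5"% (section 5.1). The SD of DIN benefit and the alternative margins are assumptions. Write m for the margin. Using the normal approximation:

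- Half-width of the 95% confidence interval: h = 1.96 × SD × √(2/30).
- Largest observed self-fit deficit that still passes: m − h.

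For a given SD, changing the margin from 1.8 to m moves this limit by |1.8 − m|, because h cancels. With m = 1.5 the shift is 0.3 dB; with m = 1.0 it is 0.8 dB. A margin wider than 1.8 would move the limit the other way by m − 1.8.

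Example at an assumed SD of 2.5 dB:

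- h = 1.96 × 2.5 × 0.2582 = 1.27 dB.
- With m = 1.8, an observed deficit of up to 0.53 dB passes.
- With m = 1.0, the limit is 1.0 − 1.27 = −0.27 dB, so the self-fit arm would have to be observed at least 0.27 dB better.

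Any observed result between these two limits changes its verdict with the margin alone.

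**Could 30 per arm support a different margin?** Power at a true difference of zero is Φ(m / (SD × √(2/30)) − 1.96).

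| Assumed SD | m = 1.8 | m = 1.5 | m = 1.0 |
|---|---|---|---|
| 1.5 dB | 99.6% | 97.2% | 73.3% |
| 2.5 dB | 79.6% | 64.2% | 34.1% |

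The largest SD that keeps 80% power is m / ((1.96 + 0.84) × 0.2582): 2.49 dB for m = 1.8, 2.07 dB for m = 1.5 and 1.38 dB for m = 1.0.

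**Does the planned analysis use the margin?** No. Section 5.3 (behavioral outcome measures) plans a t-test or a Mann-Whitney U test for a difference between groups. The 1.8 dB enters neither, for either speech test.

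**The case against.** Several points on the other side are fair.

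- **A threshold exists.** A reader might infer that the DIN has no valid threshold, or that 1.8 dB is too lenient for it. The documents support neither. A number is stated, and nothing in them shows whether it is too wide or too narrow. What is missing is the justification.
- **Score spread does not make a margin lenient or strict.** A reader might compute that a self-fit arm truly 1 dB worse would pass in 86%, 53%, 33% or 17% of trials if the SD were 1, 1.5, 2 or 3 dB, and take this as the size of the defect. It is not. A 1 dB deficit lies inside a 1.8 dB margin, so passing is the correct decision under the stated hypothesis. The range is ordinary power falling as an assumed SD rises, and it would look the same for the QuickSIN. At a true deficit of exactly 1.8 dB the pass rate is 2.5% at every SD.
- **The difference in score definition is a weak argument.** The hypothesis concerns improvement. If the normal-hearing reference in SNR loss is a fixed constant, it cancels when aided is subtracted from unaided. The difference in speech material remains.
- **A critical difference is itself a debatable basis for a margin on a group mean.** It describes error in a single score, so a noisier test would earn a wider margin. This applies equally to the QuickSIN and the IOI-HA. It is a reason to allow a DIN margin based on an important difference instead.
- **The margin is not applied in section 5.3 at all.** This is a wider gap, but it does not remove the present one. Once a confidence-interval comparison is added, the DIN would still be judged against a limit taken from another test.

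**Conclusion.** The point holds in a limited form. The 1.8 dB margin for the DIN rests only on the QuickSIN critical difference, and no section bridges the two tests. The plan otherwise sets each margin on its own instrument's scale, so the DIN departs from the plan's own practice.

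No corrected value can be given, and none should be implied. The calculation above shows only that the verdict on the DIN can turn on the choice of margin; its SDs and alternative margins are assumptions.

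Priority is low. The DIN is one of two tests in a secondary hypothesis, and the primary claim on the APHAB does not depend on it.

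**What to change.** 1. Split the speech hypothesis in section 4.3 into one for the QuickSIN and one for the DIN. Keep 1.8 dB for the QuickSIN only.
2. Before analysis, state a DIN margin with a DIN-based reason: the DIN's own critical difference, or an important difference in DIN dB. The sources cited in section 4.2.2 are the first place to look. Their numbers (5 and 6) do not correspond to DIN papers in the five-entry list at the end of the document. A separate list may exist outside the copy I have, so I could not check whether they give a usable value.
3. In section 5.3, add the 95% confidence interval for the between-group difference in DIN benefit and compare it with the margin. Define benefit as unaided minus aided, as is done for the APHAB; the present sentence for the speech tests names the aided score twice. The QuickSIN needs the same interval if its margin is to be used.
4. If no DIN-based margin can be justified, report the DIN difference with its 95% confidence interval and make no non-inferiority claim on it.

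The cost is SAP wording and one interval per visit, with no new participants, visits or measurements. The downside is that the DIN result may become descriptive. If the justified margin is narrower than 1.8 dB, 30 per arm may also be too few to meet it.

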# 5. Statistical analyses

# 5.1. Level of statistical significance

Final analyses of the primary and secondary outcomes will be analysed using a two-sided significance level of 5%.

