# Behavioral outcome measures

Speech recognition scores will be conducted at baseline and at the 2- and 6-week follow ups. Raw scores will be gathered (continuous variables). Additionally benefit scores will be determined by subtracting aided from aided scores. All variables are continuous and will be assessed for normality. For non-normally distributed variables, non-parametric comparisons between groups will be completed using the Mann Whitney *U* test. For normally distributed variables, comparisons will be done using the independent samples *t*-test.

Effect sizes will be calculated for normally distributed variables, where differences were significant. Cohen's *d* is the primary metric for determining effect sizes of normally distributed variables, for which the values of 0.8, 0.5 and 0.2 are interpreted as large, medium and small effect sizes, respectively. The following formula will be used:

$$d = \frac{M1 - M2}{SDpooled}$$

Effect sizes for non-normally distributed variables will be calculated using effect size r for non-parametric tests, calculated using the following formula:

$$z/\sqrt{N}$$

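### Section 5.3 reads as testing ten speech-in-noise variables at 5% each, although the hypotheses in section 4.3 cover only four

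*Combined protocol and SAP*

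**What the plan says.** Section 5.1 sets one level for all outcomes: "Final analyses of the primary and secondary outcomes will be analysed using a two-sided significance level of 5" per cent. No section gives a multiplicity adjustment, a testing order, or a statement that secondary results are exploratory.

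There are two speech measures. Section 4.2.2 says that "in addition to the QuickSIN, speech-in-noise performance will be measured using the South African English Digits-in-Noise test (DIN").

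Section 5.3, under Behavioral outcome measures, builds the list of variables in four steps:

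- The occasions are three: "Speech recognition scores will be conducted at baseline and at the 2- and 6-week follow ups".
- The scores on each occasion are kept as analysis variables in their own right, being described as raw and continuous.
- Derived scores are then added to the list: "Additionally benefit scores will be determined by subtracting aided from aided scores". This is evidently a slip for unaided minus aided, which is how the APHAB paragraph of the same section defines benefit.
- The scope is the whole list: "All variables are continuous and will be assessed for normality".

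Where a variable proves non-normal, "non-parametric comparisons between groups will be completed using the Mann Whitney" procedure; normal variables go to an independent-samples t-test. Neither comparison sentence names a time point or leaves any variable out. For normally distributed variables, Cohen's d is reported only where the group difference is significant.

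Section 4.3 is narrower. Its speech hypothesis concerns improvement on QuickSIN and DIN at 2 and 6 weeks, with a 1.8 dB margin. For the other secondary endpoint, "IOI-HA (secondary endpoint) will be conducted at 2- and 6-weeks post hearing aid fitting", and section 4.3 applies a one-point margin to all of its scales without saying how many there are.

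The baseline characteristics listed in section 5.3 are summarised descriptively by group. QuickSIN and DIN scores are not on that list.

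**The concern.** The analysis text is wider than the hypotheses it serves. Six of the ten speech comparisons (two at baseline, four of raw follow-up scores) answer no stated hypothesis, yet each can yield a significant result at the same level as those that do.

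The two baseline comparisons are the least useful. Section 4.2.1 measures unaided QuickSIN before allocation, and section 4.2.2 applies the same procedure to DIN. With proper randomisation, a significant baseline difference can only be chance.

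What is at stake is how the secondary results will read. Because Cohen's d is given only for significant differences, a chance positive gains a reported effect size while its non-significant neighbours do not. The error can go either way: a false difference could flatter the self-fit device or count against it. Without a statement of how secondary results are to be weighed, a reader cannot separate the hypothesised comparisons from the incidental ones.

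**Working it through.** **The plan's own figure.** The 5% in section 5.1 is an assigned level. For one test, 1 − (1 − 0.05)^1 = 0.05, so it holds test by test. The documents state no error rate for a set of tests, so there is none to reproduce.

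**Count of speech tests** (sections 4.2, 4.3 and 5.3)

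- Raw scores: 2 measures × 3 occasions = 6, of which 2 are baseline.
- Benefit scores: 2 measures × 2 follow-ups = 4.
- Total on the plain reading of 5.3: 6 + 4 = 10.
- Without the baseline tests: 10 − 2 = 8.
- Hypothesised in 4.3: 4.

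**If the tests were independent and no true difference existed,** P(at least one false difference) = 1 − 0.95^m:

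- m = 10: 40.1%; expected false positives 10 × 0.05 = 0.5
- m = 8: 33.7%
- m = 4: 18.5%; expected false positives 4 × 0.05 = 0.2
- m = 2 (baseline pair alone): 9.75%

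**Allowing for correlation.** Independence cannot hold, because each benefit score is the difference of two raw scores on the same list. I simulated trials with 30 per arm (section 3.3), normal scores, no group difference, benefit = baseline minus aided, and two-sided t-tests at 5%. The correlation between occasions of the same measure is a, and between the two measures on the same occasion b. The documents give neither, so both are assumptions. There were 40,000 trials per row.

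| a | b | 10 tests | 8 (no baseline) | 4 (benefit only) |
|---|---|---|---|---|
| 0.4 | 0.4 | 31.9% | 28.4% | 16.8% |
| 0.5 | 0.5 | 30.7% | 27.4% | 16.1% |
| 0.7 | 0.6 | 29.3% | 26.6% | 15.7% |
| 0.8 | 0.7 | 27.2% | 25.1% | 15.3% |
| 0.8 | 0.8 | 25.6% | 23.7% | 14.1% |

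In these runs the baseline pair alone gives 8–9%.

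**IOI-HA.** With k scales there are 2k further tests. The documents do not give k. Taking k from 1 to 7 purely as an assumed range, the hypothesised secondary comparisons number 4 + 2k = 6 to 18, and the independence figure is 1 − 0.95^6 = 26.5% to 1 − 0.95^18 = 60.3%. Correlation lowers these.

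**A joint rule.** If a secondary claim requires every component to succeed, then P(all succeed) ≤ P(any given one succeeds). The chance of a false joint claim therefore cannot exceed the per-test level, and no adjustment is needed for it.

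**The case against.** The case for leaving the plan alone has four parts.

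- *The 5% is a per-test level.* This stands. Section 5.1 never promises control over the whole set, so a reader who infers that the plan breaches its own stated 5% goes too far.
- *No baseline test is ordered.* This stands in part. The sentence covering all variables is about normality, and every hypothesis concerns follow-up. But the comparison sentences that follow apply to variables according to their distribution, with no exclusion. Dropping the baseline pair still leaves eight tests and about 24–28%.
- *Section 4.3 already says what matters.* This stands. A reader might infer that the plan never says which speech score or visit carries the hypothesis, but section 4.3 names improvement and both visits. The gap is that section 5.3 does not restrict testing accordingly.
- *The secondary claims are joint.* This stands on the wording of section 4.3: all IOI-HA scales, and QuickSIN together with DIN. A reader might infer that one favourable score would suffice for a non-inferiority claim; the documents do not say so, and a joint rule would not inflate such claims. Section 5, however, states no joint rule and tests each score separately for a difference.

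A larger headline is also tempting: 12 to 24 secondary tests with a 46% to 71% chance of a false positive. It depends on an IOI-HA scale count that the documents do not give and on an independence that cannot hold.

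**Conclusion.** The concern holds in a limited form. Read plainly, section 5.3 tests ten speech variables at 5% each where section 4.3 needs four. That raises the chance of at least one false speech difference from about 14–17% to about 26–32%. Both ranges assume that no true difference exists, correlations of 0.4 to 0.8 and 30 per arm; the independence figures are 19% and 40%. The ten includes two baseline tests, which the wording allows but does not name.

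The figures concern false differences from the planned difference tests, not false non-inferiority conclusions. A reader might also infer that the secondary endpoints must be gated on the primary, or that one visit must be made decisive. The documents require neither. Section 3.2.2 gives the visits different purposes: the first two weeks isolate the fitting, and the second phase allows support.

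**What to change.** **Section 5.3.** Limit the formal speech comparisons to QuickSIN and DIN benefit at 2 and 6 weeks. Correct the definition of benefit in that paragraph, since it becomes the tested variable. Present baseline speech scores descriptively, as is done for the other baseline data, and raw follow-up scores as group differences with 95% confidence intervals. Give no p-values for either.

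**Section 5.1.** State that the secondary claims are joint, in line with section 4.3: all IOI-HA scales for one, and QuickSIN and DIN both within margin for the other, each at both visits. State that any single-score result is supportive and unadjusted for multiplicity. Give the number of IOI-HA scales.

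A fixed sequence opened by success on the primary endpoint is optional. No single visit should be made decisive.

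**Cost.** No new data, and fewer p-values to report. The speech and labelling changes are wording only. The joint claims also need each result compared with its margin, which section 5 does not yet set out and must be added for these claims to be assessable.
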